### 5.2.2. Analyses for Continuous Data

The *C difficile* toxin A- and toxin B-specific neutralizing antibody levels at each blood sampling time point will be summarized by GMCs and the associated 95% CIs for each vaccine group. The GMC will be calculated as the mean of the assay results after making the logarithm transformation and then back transformation to its original scale. Two-sided 95% CIs will be constructed by back transformation of the CI for the mean of the logarithmically transformed assay results computed based on the Student t distribution.

For each *C difficile* toxin A- and toxin B-specific neutralizing antibody levels, a line plot of the GMC and the associated 95% CI over the sampling time points will be provided by vaccine group, separately for each assigned 3-dose regimen in the original planned stage and for the fourth dose in the extension stage.

The GMFRs in toxin A– and toxin B–specific neutralizing antibody levels from before vaccination to after vaccination will be summarized for each vaccine group by geometric means and associated CIs at all postbaseline blood sampling time points. These CIs are also computed by back transformation of the CIs using the Student t distribution for the mean difference of measures on the logarithmically transformed assay results.

For the originally planned stage, empirical reverse cumulative distribution curves (RCDCs) will be presented graphically for each *C difficile* toxin A– and toxin B–specific neutralizing antibody levels for each vaccine group (including placebo) at Day 37 (Visit 5) and all blood sampling time points after Day 37 for the Day 1, 8, and 30 regimen, and at Month 7 (Visit 7) and all blood sampling time points after Month 7 for the Month 0, 1, and 6 regimen.

For the extension stage, RCDCs will also be presented graphically for each *C difficile* toxin A– and toxin B–specific neutralizing antibody level for each vaccine group at Day 8 after Vaccination 4 (Visit 10) and all blood sampling time points after Visit 10.

### **5.3. Methods to Manage Missing Data**

#### **5.3.1. Immunogenicity Data**

For any *C difficile* toxin A– or toxin B–specific neutralizing antibody level that is below the LLOQ, the lower limit of detection (LOD), defined as  $0.5 \times \text{LLOQ}$ , will be assigned. No other missing assay data will be imputed in the analyses. All immunogenicity analyses will be performed after the imputation of the antibody levels that are below the LLOQ.

For each *C difficile* toxin A– or toxin B–specific neutralizing antibody result, the number of subjects with missing values at each blood sampling point will be provided.

#### **5.3.2. Safety Data**

Handling of missing information related to safety data, such as missing or partially missing date, will be in accordance with Pfizer reporting standards.

For derived variables in reactogenicity data, if any day of the 7-day e-diary is available, the “Day 1 – Day 7” data will be considered as nonmissing for analyses after Vaccination 1 on the Day 1, 8, and 30 regimen and if any of the 14-day e-diary is available, the “Day 1 – Day 14” data will be considered as nonmissing for analyses after Vaccinations 2 and 3 on the Day 1, 8, and 30 regimen, and after each vaccination on the Month 0, 1, and 6 regimen, and Vaccination 4 in the extension stage. The proportion of subjects with missing reactogenicity data will also be summarized by each vaccination for each vaccine group. The denominator will be the number of subjects who receive the scheduled vaccination.

## **6. ANALYSES AND SUMMARIES**

### **6.1. Primary Endpoint(s)**

#### **6.1.1. Primary Immunogenicity Endpoints**

##### **6.1.1.1. Primary Analysis**

**Endpoints:** Primary immunogenicity endpoints in [Section 3.1.1](#)

- Analysis time points:  
For the Day 1, 8, and 30 regimen: Day 37  
For the Month 0, 1, and 6 regimen: Month 7
- Analysis populations: Evaluable immunogenicity and mITT populations
- Analysis methodology: See [Section 5.2.1](#)
- Supporting objective: Primary immunogenicity objectives

#### **Reporting Results:**

The numerator and denominator used for the proportion and associated 95% CI at Day 37 or Month 7 will be presented for each vaccine group in each regimen (Days 1, 8, and 30 or Months 0, 1, and 6).

#### **Figures:**

The antibody response line plot of proportions and the associated 95% CI at Day 37 or Month 7 will be provided by vaccine group, separately for each regimen.

### **6.1.2. Primary Safety Endpoints**

**Endpoints:** Primary safety endpoints in [Section 3.1.2](#)

- Analysis time points:  
Local reactions and systemic events: Up to 14 days following each vaccination  
AEs: From the first vaccination up to 28 days after the third vaccination  
SAEs: From the first vaccination until 6 months after the third vaccination
- Analysis population: Safety population
- Analysis methodology: Descriptive; see [Section 5.2.1](#)
- Supporting objective: Primary safety objective

## **Reporting Results:**

The number, proportion, and associated 95% CI will be presented for each vaccine group in each regimen (Days 1, 8, and 30 or Months 0, 1, and 6).

### **6.2. Secondary Endpoints**

#### **6.2.1. Secondary Immunogenicity Endpoints**

**Endpoints:** Secondary immunogenicity endpoints described in [Section 3.2](#)

**Endpoints:** GMCs for toxin A– and toxin B–specific neutralizing antibody levels

- Analysis time points:

Original planned stage:

For the Day 1, 8, and 30 regimen: Days 1, 8, 15, 30, and 37 and Months 2, 4, 7, and 13

For the Month 0, 1, and 6 regimen: Days 1, 30, and 37, Months 2 and 6, Day 187, and Months 7, 12, and 18

Extension stage:

at the fourth dose (immediately before the fourth dose), at Days 8 and 30 after the fourth dose, and at Months 6, 12, 18, 24, 30, and 36 after the fourth dose:

- Analysis populations: mITT and evaluable immunogenicity populations
- Analysis methodology: See [Section 5.2.2](#)
- Supporting objective: Secondary immunogenicity objective

## **Reporting Results:**

The number, GMC, and associated 95% CI at the above analysis time points will be presented for each vaccine group in each regimen (Days 1, 8, and 30 or Months 0, 1, and 6) separately for the originally planned stage and the extension stage

## **Figures:**

The antibody-response line plot of GMCs and the associated 95% CI for each toxin A– and toxin B–specific neutralizing antibody level at the above analysis time points will be presented by vaccine group, separately for each regimen in the originally planned stage and the extension stage.

**Endpoints:** GMFRs from baseline in toxin A– and toxin B–specific neutralizing antibody levels

- Analysis time points:

Original planned stage:

For the Day 1, 8, and 30 regimen: Days 8, 15, 30, and 37, and Months 2, 4, 7 and 13  
For the Month 0, 1, and 6 regimen: Days 30 and 37, Months 2 and 6, Day 187, and Months 7, 12, and 18

Extension stage:

at the fourth dose (immediately before the fourth dose), at Days 8 and 30 after the fourth dose, and at Months 6, 12, 18, 24, 30, and 36 after the fourth dose

- Analysis populations: mITT and evaluable immunogenicity populations
- Analysis methodology: See [Section 5.2.2](#)
- Supporting objective: Secondary immunogenicity objective

### **Reporting Results:**

The sample size, GMFR, and associated 95% CI at the above analysis time points will be presented for each vaccine group in each 3-dose regimen (Days 1, 8, and 30 or Months 0, 1, and 6) separately for the originally planned stage and the extension stage.

**Endpoints:** Proportions with  $\geq 4$ -fold,  $\geq 8$ -fold,  $\geq 16$ -fold, and  $\geq 32$  fold rises from baseline in toxin A-specific, toxin B-specific, and both toxin A- and toxin B-specific neutralizing antibody levels

- Analysis time points:

Original planned stage:

For the Day 1, 8, and 30 regimen: Days 8, 15, 30, and 37 and Months 2, 4, 7, and 13  
For the Month 0, 1, and 6 regimen: Days 30 and 37, Months 2 and 6, Day 187, and Months 7, 12, and 18

Extension stage:

at the fourth dose (immediately before the fourth dose), at Days 8 and 30 after the fourth dose, and at Months 6, 12, 18, 24, 30, and 36 after the fourth dose

- Analysis populations: mITT and evaluable immunogenicity populations
- Analysis methodology: See [Section 5.2.1](#)
- Supporting objective: Secondary immunogenicity objective

### **Reporting Results:**

The numerator and denominator used for proportion, proportion, and associated 95% CI at the above analysis time points will be presented for each vaccine group in each regimen (Days 1, 8, and 30 or Months 0, 1, and 6) separately for the originally planned stage and the extension stage.

**Endpoints:** Proportions with toxin A-specific neutralizing antibody levels  $\geq$  the specified threshold for toxin A; proportions with toxin B-specific neutralizing antibody levels  $\geq$  the specified threshold for toxin B; proportions with both toxin A- and toxin B-specific neutralizing antibody levels  $\geq$  the specified threshold for toxin A and the specified threshold for toxin B, respectively.

- Analysis time points:

Original planned stage:

For the Day 1, 8, and 30 regimen: Days 1, 8, 15, and 30 and Months 2, 4, 7, and 13

For the Month 0, 1, and 6 regimen: Days 1, 30, and 37, Months 2 and 6, Day 187, and Months 12 and 18

Extension stage:

at the fourth (immediately before the fourth dose), at Days 8 and 30 after the fourth dose, and at Months 6, 12, 18, 24, 30, and 36 after the fourth dose

- Analysis populations: mITT and evaluable immunogenicity populations
- Analysis methodology: See [Section 5.2.1](#)
- Supporting objective: Secondary immunogenicity objective

### **Reporting Results:**

The numerator and denominator used for proportion, the proportion, and associated 95% CI at the above analysis time points will be presented for each vaccine group in each regimen (Days 1, 8, and 30 or Months 0, 1, and 6) separately for the originally planned stage and the extension stage.

### **Figures:**

The antibody-response line plot of proportions and the associated 95% CI at the above analysis time points will be presented by vaccine group, separately for each regimen in the originally planned stage and the extension stage.

#### **6.2.2. Secondary Safety Endpoints**

**Endpoints:** Secondary safety endpoints in [Section 3.2.2](#)

- Analysis time points:  
Local reactions and systemic events: Up to 14 days following fourth vaccination  
AEs: From the time of the fourth vaccination up to 28 days after the fourth vaccination  
SAEs: From the time of the fourth vaccination up to 28 days after the fourth vaccination
- Analysis population: Safety population
- Analysis methodology: Descriptive; see [Section 5.2.1](#)
- Supporting objective: Secondary safety objective

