#### **6.3.4. Visit 12: Month 6 After Vaccination 4 ( $\pm 30$ Days)**

- Ensure that the subject continues to be eligible for the study (see [Section 6.5](#)).
- Based on clinical evaluation, determine whether any SAEs have occurred since the last study visit. Record and report findings as described in [Section 8](#) and the [Schedule of Activities](#). Review AEs that were ongoing from the previous visit and record their stop dates or confirm if they are still continuing. In addition, any AEs or research-related injuries (RRIs) occurring up to 48 hours after the blood draw will be recorded.
- Collect a blood sample of approximately 20 mL for immunogenicity testing ([Section 7.2](#)).
- For subjects at designated sites who have consented to the additional blood draw, collect a whole blood sample of approximately 20 to 50 mL for exploratory testing (see details below\*).
- Schedule an appointment for the subject to return for the next study visit.
- Complete the source documents.
- Complete the CRF.

\*For sites to participate in collection of blood samples for exploratory purposes, the following additional procedures will be completed:

Obtain written informed consent from subjects agreeing to the additional blood draw.

Obtain additional blood sample of 20 to 50 mL for exploratory purposes. Maximum amount of blood to be obtained at this visit for those subjects participating is up to 70 mL.

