### **8.2. Reporting Period**

For SAEs, the active reporting period to Pfizer or its designated representative begins from the time that the subject provides informed consent, which is obtained prior to the subject's participation in the study, ie, prior to undergoing any study-related procedure and/or receiving investigational product, through and including Visit 8 (Month 7 for subjects on the Day 1, 8, and 30 regimen and Month 12 for subjects on the Month 0, 1, and 6 regimen).

During the extension stage, the active reporting period for SAEs to Pfizer or its designated representative begins from the time that the subject provides informed consent for the extension stage, which is obtained prior to the subject's participation in the extension stage, ie, prior to undergoing any study-related procedure and/or receiving investigational product, through and including Visit 12 (6 months after the fourth dose).

SAEs occurring to a subject after the active reporting period has ended should be reported to the sponsor if the investigator becomes aware of them; at a minimum, all SAEs that the investigator believes have at least a reasonable possibility of being related to investigational product are to be reported to the sponsor.

All AEs should be recorded on the CRF from the time the subject provides informed consent until 1 month after the third vaccination (Visit 6 [Month 2] for subjects on the Day 1, 8, and 30 regimen and Visit 7 [Month 7] for subjects on the Month 0, 1, and 6 regimen).

During the extension stage, all AEs should be recorded on the CRF from the time the subject provides informed consent until 1 month after the fourth vaccination (Visit 11).

Any AE occurring up to 48 hours after each subsequent blood draw (Visit 6 [Month 2], Visit 7 [Month 4], Visit 8 [Month 7], and Visit 9 [Month 13] for subjects on the Day 1, 8, and 30 regimen and Visit 7 [Month 7], Visit 8 [Month 12], and Visit 9 [Month 18] for subjects on the Month 0, 1, and 6 regimen) must be recorded on the CRF.

During the latter part of the extension stage, any AE (including RRIs) occurring up to 48 hours after the blood draw at Visits 12, 13, 14, 15, 16, and 17 (Months 6, 12, 18, 24, 30, and 36 after the fourth dose) must be recorded on the CRF.

The investigator is required to assess whether the AE may be related to the subject's participation in the study.

CCI

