### 3.2.2. Secondary Safety Endpoints

- Numbers and proportions of subjects reporting local reactions (pain, erythema, and induration) and their severity, as self-reported on e-diaries for 14 days following the fourth vaccination.
- Numbers and proportions of subjects reporting systemic events (fever, vomiting, diarrhea, headache, fatigue, new or worsening muscle pain, and new or worsening joint pain) and their severity, as self-reported on e-diaries for 14 days following the fourth vaccination.
- Numbers and proportions of subjects reporting AEs from the time of the fourth vaccination up to 28 days after the fourth vaccination categorized according to MedDRA.
- Numbers and proportions of subjects reporting SAEs from the time of the fourth vaccination until 6 months after the fourth dose of vaccine, categorized according to MedDRA.

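### SAP 6.2.2 stops the fourth-dose SAE analysis at 28 days, although the endpoint it cites in SAP 3.2.2 runs to 6 months

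*SAP*

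**What the plan says.** SAP 6.2.2 (Secondary Safety Endpoints) states that its object is the set of endpoints in SAP 3.2.2. Its time-point list then gives two entries with the same window:

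- for AEs: "AEs: From the time of the fourth vaccination up to 28 days after the fourth vaccination";
- for SAEs: "SAEs: From the time of the fourth vaccination up to 28 days after the fourth vaccination".

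SAP 3.2.2, the section it cites, treats the two differently. The AE endpoint covers "AEs from the time of the fourth vaccination up to 28 days after the fourth vaccination categorized according to MedDRA". The SAE endpoint covers "SAEs from the time of the fourth vaccination until 6 months after the fourth dose of vaccine". Protocol 2.2.4 has the same 6-month SAE endpoint.

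Data collection follows the longer window. Protocol 8.2 keeps active SAE reporting in the extension stage open through Visit 12, 6 months after Dose 4. The extension-stage Schedule of Activities marks SAE recording at Visits 9, 10, 11 and 12. At Visit 12, Protocol 6.3.4 tells the site to "determine whether any SAEs have occurred since the last study visit".

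**The concern.** One endpoint has two analysis windows within the same SAP. SAP 6.2.2 is the section that specifies the analysis, so its time-point line is what a programmer would naturally implement. On that reading, an SAE occurring between Day 29 and Month 6 after the fourth dose is collected but does not count in the endpoint.

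Safety and tolerability of the fourth dose is the only secondary safety objective, and SAEs are a named component of it. Two analysts working from the same plan and the same data could report different SAE proportions, each with text to point to.

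**Working it through.** The plan states no figure to reproduce here. The check compares the stated windows and then measures the gap between them.

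**Step 1: compare the windows.**

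| Source | AEs | SAEs |
|---|---|---|
| SAP 3.2.2, endpoint definition, Dose 4 | 28 days after Dose 4 | 6 months after Dose 4 |
| Protocol 2.2.4, endpoint definition, Dose 4 | 28 days after Dose 4 | 6 months after Dose 4 |
| Protocol 8.2, collection, extension stage | 1 month after Dose 4 (Visit 11) | Visit 12, 6 months after Dose 4 |
| SAP 6.1.2, analysis, Doses 1 to 3 | 28 days after Dose 3 | 6 months after Dose 3 |
| SAP 6.2.2, analysis, Dose 4 | 28 days after Dose 4 | **28 days after Dose 4** |

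Only the last SAE entry departs from the pattern. The matching section for the first three doses, SAP 6.1.2, keeps the windows apart, with "SAEs: From the first vaccination until 6 months after the third vaccination" for SAEs.

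**Step 2: look for text that settles the conflict.**

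- SAP 6.5 and 6.5.1 give no SAE window, and neither does SAP 5.2.1, the methods section that 6.2.2 cites.
- SAP 5.1 promises estimates and confidence intervals for all safety endpoints. This supports the 3.2.2 definition but does not withdraw the 28-day line.
- SAP Section 2 allows the SAP to modify the protocol. That does not explain the line, because SAP 3.2.2 itself keeps 6 months, and the SAP's table of major changes declares no shorter SAE window.

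**Step 3: share of the window left out on a literal reading.** Taking 6 months as about 183 days:

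- Days left out = 183 − 28 = 155.
- Share = 155/183 = 0.847, about 85%.

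Visit 12 has a ±30-day window. If collection ends anywhere from 150 to 210 days (180 ± 30), the share is 1 − 28/150 = 81.3% to 1 − 28/210 = 86.7%. These are shares of time, not of events.

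**Step 4: illustrative effect on the reported proportion.** The documents give no SAE rate, so every rate below is an assumption. Let r be the true 6-month proportion of subjects with at least one SAE.

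With constant hazard, λ = −ln(1 − r)/183, and the 28-day proportion is 1 − exp(−28λ):

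| Assumed r | 28-day proportion |
|---|---|
| 3% | 0.465% |
| 5% | 0.782% |
| 8% | 1.268% |

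If SAEs cluster early, the 28-day proportion is r × f, where f is the share of subjects with an SAE whose first one falls by Day 28. For r = 5%:

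- f = 0.30 gives 0.05 × 0.30 = 1.5%.
- f = 0.50 gives 0.05 × 0.50 = 2.5%.

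To put this in subjects, take 366 as an upper limit for those given active vaccine at Dose 4. It is half of the 4 × 183 = 732 originally planned for active vaccine, under the 1:1 rerandomization in Protocol 1.2.3, and assumes that all of them enter the extension. With r = 5% and constant hazard, 366 × 0.05 = 18.3 subjects with an SAE are expected over 6 months and 366 × 0.00782 = 2.9 within 28 days. About 15 would not be counted.

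**The case against.** The best case against giving this much weight is that the plan as a whole points to 6 months. The endpoint definition, the cross-reference in 6.2.2, the general rule in SAP 5.1 and Protocol 2.2.4 all agree. The single contrary line repeats the AE line above it, so a copying slip is the likeliest cause, though that is an inference. An analyst who follows the cross-reference would get the right answer.

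The consequence is also limited. The endpoint is secondary and descriptive, with no hypothesis test. The short window would apply equally to every fourth-dose group, so it does not by itself favour vaccine or placebo. SAE collection and expedited reporting continue through Visit 12, and the external data monitoring committee's reviews of unblinded safety data, about twice a year, do not depend on this line.

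The endpoint also counts subjects, not events. A subject whose first SAE falls by Day 28 counts under either window, so the 28-day proportion falls below the 6-month one only if some subject has a first SAE after Day 28.

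All of this stands and bounds the importance of the point. None of it removes the conflicting line, which is an operative instruction in the section that governs the analysis.

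**Conclusion.** The inconsistency is real and should be fixed. The contradiction is visible in the text and rests on no assumption: SAP 6.2.2 sets a 28-day SAE window for an endpoint that SAP 3.2.2 and Protocol 2.2.4 define over 6 months.

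Its effect depends on the 28-day line being followed literally. In that case about 85% of the defined window (81% to 87% across the Visit 12 window) is left out of this summary, and the reported SAE proportion is lower than or equal to the defined one. The proportions in Step 4 are illustrations that depend on assumed rates and timing. If the SAP 3.2.2 definition is followed instead, the result is correct.

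**What to change.** In SAP 6.2.2, replace the SAE time-point line with the window from SAP 3.2.2: "SAEs from the time of the fourth vaccination until 6 months after the fourth dose of vaccine". Leave the AE line at 28 days, which already matches its definition. Make the change before the supplemental CSR analysis and record it in the SAP's table of changes.

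The cost is one line of SAP text. No new data, visits or protocol changes are needed, because SAEs are already collected through Visit 12 and Protocol 2.2.4 already states the 6-month endpoint.

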### **Reporting Results:**

The number, proportion, and associated 95% CI will be presented for each vaccine group in each originally assigned regimen (Days 1, 8, and 30 or Months 0, 1, and 6).

[figure not shown]
[figure not shown]
6.3. **CCI**

CCI

**Table 7.**

**CCI**

**Table 7.**

CCI

CCI

Subgroup analyses of primary and selected secondary immunogenicity endpoints (proportions equal to or above the prespecified threshold, proportions achieving  $\geq 4$  fold from baseline and GMCs) will be conducted by age cohorts (65 to 69 years, 70 to 74 years, 75 to 79 years, and 80 to 85 years), separately for each regimen, to explore the impact of age on the immunogenicity results. Similar subgroup analyses (proportions equal to or above the prespecified threshold, proportions achieving  $\geq 4$  fold from baseline and GMCs) will be conducted by the combination of age cohorts and baseline status. All subgroup analyses will be performed based on the evaluable immunogenicity population.

For the statistical analysis related to endpoints of proportions of subjects achieving 1) toxin A-specific, 2) toxin B-specific, and 3) toxin A- and toxin B-specific neutralizing antibody levels  $\geq$  the specified thresholds defined in [Section 3.1.1](#), alternative levels/thresholds may be considered.

